Objectives	To establish whether women affected by intrahepatic cholestasis of pregnancy (ICP) and gestational diabetes mellitus (GDM) are predisposed towards developing metabolic disease in pregnancy and in later life. We will do this by measuring metabolic markers and assessing glucose homeostasis.
Population	Pregnant and non pregnant parous women
Eligibility	Pregnant and non pregnant women who have been affected by ICP and GDM together with matched controls

GLOSSARY OF ABBREVIATIONS

OC	Obstetric Cholestasis
ICP	Intrahepatic Cholestasis of Pregnancy
AE	Adverse Event
SAE	Serious Adverse Event
GCP	Good Clinical Practice
CI	Chief Investigator
GDM	Gestational Diabetes Mellitus

1. Background

CLINICAL FEATURES OF INTRAHEPATIC CHOLESTASIS OF PREGNANCY:

Intrahepatic cholestasis of pregnancy (ICP), is a pregnancy-specific liver disorder which typically presents with maternal pruritus (itching) in late pregnancy and affects about 0.7% of women in the UK. Biochemically, it is characterised by liver dysfunction with raised serum bile acids, and clinically by a significantly increased incidence of fetal complications, including spontaneous preterm labour, fetal distress, meconium staining of the amniotic fluid and sudden fetal death (Geenes and Williamson 2009).

The cause of ICP is complex and not fully understood. In addition the pathological mechanisms behind the adverse fetal outcomes have not been elucidated. The maternal disease is likely to be caused by interaction between sex hormone metabolites and bile acids in genetically susceptible women (Abu-Hayyeh et al. 2010). To date, we and others have identified genetic variation in several biliary transporters e.g. ABCB4, ATP8B1, ABCB11 and the main bile acid receptor, FXR, that predispose women to the disease (Dixon et al., 2000; Mullenbach et al., 2005; Pauli-Magnus et al., 2004; Van Mil et al, 2007; Dixon et al. 2009). Due to their inherent toxicity, bile acids are also likely to be responsible for the fetal component of the disease. Consistent with this the incidence of fetal complications has been shown to be increased in pregnancies where the levels exceed 40 uMol /L (Glantz et al., 2004). There are currently several theories about how bile acids may affect fetal wellbeing; with regard to the increased incidence of spontaneous prematurity, they have been shown to cause premature delivery in sheep (Campos et al., 1986), and increased myometrial contractility in response to oxytocin (Germain et al., 2003; Israel et al., 1986). Furthermore, bile acids are also known to cause increased colonic motility in rabbits (Snape et al., 1980) and cardiac dysrhythmias in rats (Williamson et al., 2001), which could explain meconium staining of the amniotic fluid and sudden fetal death respectively. While it is known that bile acids can be transported by proteins in the placenta, the precise role of the placenta in bile, lipid and glucose metabolism is not known. Our group has demonstrated that cholestasis alters lipid pathways in mouse placentas (unpublished data) but this has not been studied in humans.

BILE ACID HOMEOSTASIS:

Bile acids are the end product of hepatic cholesterol metabolism and act as the main route of excretion for cholesterol. In the adult human two primary bile acids are produced by the liver, i.e. cholic acid and chenodeoxycholic acid. There is some evidence that maternal bile acids gradually rise with advancing gestation, but they usually remain within normal limits (< 14 uMol /L) (Fulton et al., 1983; Pascual et al., 2002). This is in contrast to an ICP pregnancy, where maternal bile acids may be raised to 100 times the upper limit of normal (Walker et al., 2002). In OC, elevated levels of bile acids are also found in the fetal circulation (Laatikainen, 1975).

THE ROLE OF BILE ACIDS IN LIPID AND GLUCOSE METABOLISM:

There is accumulating evidence that FXR, the nuclear hormone receptor responsible for regulation of bile acid homeostasis, also plays a role in the regulation of lipid and glucose metabolism. FXR null mice have been shown to have abnormal blood lipid profiles including elevated plasma cholesterol, low density lipoprotein, high density lipoprotein and triglyceride levels (Ma, 2006). They also exhibit glucose intolerance and reduced insulin sensitivity (Zhang, 2006). Furthermore, ICP patients have raised levels of cholesterol and other lipid parameters (Dann et al. 2006). Specifically, the serum concentrations of low-density lipoprotein (LDL), apolipoprotein B-100, cholesterol and total cholesterol were markedly increased in women with ICP. They have also been shown to have impaired glucose tolerance (Wójcicka-Jagodzińska et al. 1989). Recent data from our group (Martineau et al. 2014, 2015) and others (Marschall et al. 2014) have shown that women with ICP have increased rates of GDM, and implicate raised serum bile acids in susceptibility to diabetes mellitus. Therefore this study will also include women with ICP and superimposed GDM in addition to women with GDM in the absence of ICP. This will enable us to evaluate the impact of cholestasis on the onset of diabetes mellitus in pregnant women.

In cholestasis bile acids accumulate in the liver, and this results in the induction of pathways that enhance bile acid excretion. This may also cause abnormal cholesterol and triglyceride levels. Bile acids also signal via FXR in the gut. Bile acids are stored in the gallbladder in the fasting state and released following ingestion of a meal. Once bile acids are in the intestine they are transported into enterocytes (gut cells) where they activate FXR which causes production and release of the hormone FGF19. FGF19 binds the FGF4 receptor on hepatocytes, and signals (via the jnk kinase pathway) to suppress cholesterol 7 alpha-hydroxylase (CYP7A1), a critical rate-limiting enzyme in synthesis of bile acids from cholesterol. There have been no studies of the gut-liver axis in pregnancy, but we hypothesise that abnormal bile acid signalling causes raised cholesterol in addition to increased serum bile acids.

Bile acids also bind the G-protein-coupled receptor (TGR5). In the gut this results in release of glucagon-like peptide-1 (GLP-1)(Thomas et al. 2009). GLP-1 is an anti-diabetic hormone that increases glucose-dependent insulin production and decreases glucagon production by the pancreas. To date, there have been no studies of the relationship between cholestasis and GDM and the levels of other fasting gut hormones that may influence glucose and lipid metabolism in pregnancy.

IMPORTANCE:

ICP is known to cause abnormal bile acid homeostasis and to be associated with an increased risk of diseases of the biliary system in later life. There have been small studies (Dann et al. 2006; Wójcicka-Jagodzińska et al. 1989) suggesting that it causes dyslipidaemia (raised lipids) and impaired glucose tolerance in pregnancy. However the underlying mechanisms of these abnormalities is not known. Similarly the influence of cholestasis on fetal metabolism is not known, and nor is the role of the placenta. It is also not known whether women with ICP have a predisposition to abnormal lipid and glucose homeostasis when they are not pregnant.

GDM is characterized by raised plasma glucose levels in pregnant women (in the absence of pre-pregnancy diabetes mellitus). This condition is associated with large-for-gestational age babies and obstructed labour. Women with GDM have increased risk of subsequent type 2 diabetes mellitus, and if they have this condition in a subsequent pregnancy there is an increased risk of stillbirth. This work is important to understand the causes of the metabolic abnormalities associated with ICP and GDM. If we demonstrate abnormal lipid and glucose profiles, these may be of relevance to the fetal complications of both disorders. It will also be of relevance to the future health of affected women and their children.

2. Hypothesis

There is a relationship between cholestasis and abnormalities of lipid and glucose homeostasis in the mother and baby

That there are abnormalities in bile acid, lipid and glucose homeostasis in women who have previously had ICP compared to controls.

That the placenta may play a role in bile, lipid and glucose homeostasis in ICP cases and controls

Some of the hormonal signals that cause ICP-associated GDM may also cause GDM in non-cholestatic women.

3. Study Objectives and outcomes

Objectives:

- To evaluate the relationship between bile acid, lipid and glucose metabolites in the mother and fetus in ICP, GDM and uncomplicated pregnancies.

Outcomes:

Primary Outcome

- To establish whether raised serum bile acids are associated with abnormalities in cholesterol and triglycerides in the mother and fetus

Secondary Outcome

- To establish the relationship between raised serum bile acids in the mother and fetus and abnormalities in:
 1. Glucose homeostasis
 2. Gut liver signaling hormones related to FGF 19 and C4 levels
 3. Gut hormone secretion

4. Study design

In the non pregnant group we aim to recruit 40 women and 40 matched controls.

In the pregnant women with and without ICP or GDM we aim to recruit 40 in each group together with matched controls.

Written consent will be obtained from all participants.

Potential participants (both cases and controls) will be identified from the antenatal, obstetric medical and day assessment clinics at Queen Charlotte's and Chelsea Hospital, St Mary's Hospital and other participating units. Midwives and clinicians will be able to refer women who have previously had the conditions after asking them if they would be interested in speaking to someone from the research team regarding the study. Posters will be used in clinical areas and in the cafe area by the antenatal clinic to highlight the research. Women will also be approached directly in these clinics by researchers.

Non-pregnant females may be identified through organisations such as ICP Support and from posters in gynaecology clinics and hospital areas such as the entrance lobby to the main hospital where the shop and cash machine is situated. Clinicians and nurses will

also be able to refer women to the research team after asking the patient if they would be interested in speaking to someone from the research team.

The study will be a case-control study. The pregnancy cohort will be recruited prospectively and will undergo longitudinal study. The non-pregnant participants will also be recruited prospectively but this will be a cross-sectional study.

The study will comprise of the following groups of women. In the groups that comprise pregnant women, maternal blood will be collected at delivery together with placental samples and cord blood (once delivery has taken place and the cord has been clamped and cut). The collection of these types of samples will allow the researchers to fully investigate the metabolites, bile acids and hormones implicated in the disorder together with the potential impact they may have on both mother and baby.

Group 1 are non-pregnant women who have either had normal pregnancies in the past or who have had at least one pregnancy affected by intrahepatic cholestasis of pregnancy (ICP) and/or gestational diabetes mellitus (GDM). This group should only have to attend the study for one day.

Group 2 are women who are identified in early pregnancy. They are either expected to go on to have normal pregnancies or are women with a previous history of ICP and/or GDM. These women may be asked to participate up to three times. This will mean they will need to attend for three separate days. However, this will be linked to their regular visits to the hospital.

Group 3 are women who have been diagnosed during their current pregnancy with ICP and/or GDM. These women may be asked to participate twice. This will mean they need to attend for two separate days. However, this will be linked to their regular visits to the hospital which is likely to be at least once a week.

All participants will be given a standard meal (designed by a dietitian) to eat the evening before the study day. Vegetarian and allergy needs will have been taken into account. They will then come to Queen Charlotte's & Chelsea Hospital (or other participating centres) at 8 am the following morning. Each participant will be given a choice regarding the collection of the blood samples. They can have an intravenous cannula inserted or

they can be bled separately each time or have a mixture of both procedures. For example, the first few samples could be taken separately and then a cannula could be inserted for the remaining samples that need to be collected and which are close in timing to each other. The first sample that is collected as soon as they arrive is a fasting sample.

Participants in group 1, 2 and 3 will be involved for most of the day, arriving at 8am in the morning and leaving around 4pm in the afternoon. Following the collection of the fasted sample outlined above participants will be provided with a breakfast. At one and two hours after breakfast blood samples will be taken. Finally, participants will have a standardised lunch with venous blood samples taken 15 minutes before consumption and further blood samples taken at the time of consumption and 20, 60, 120, and 180 minutes post consumption.

In total we will take 9 samples of blood from women in groups 1, 2 and 3. This will constitute a total of no more than 120 mls (approximately 9 tablespoons) of blood being taken on the day of the study.

The protocol will be performed only once for women in group 1. It will be performed twice for women in group 2 (at 11-13 weeks and 28-40 weeks). Women in group 2 who go on to develop ICP and/or GDM again in the current pregnancy will be transferred to group 3 at the time of diagnosis. Hence, it is possible that the protocol may be performed four times (11-13 weeks, third trimester, at the time of diagnosis, and 1-4 weeks after starting treatment with ursodeoxycholic acid). In reality this is unlikely to happen and hasn't so far in the study but we would like to retain this option should a participant meet the criteria and be happy to take part four times. For women in group 3 the protocol will be performed twice (at diagnosis and 1-4 weeks after starting treatment with ursodeoxycholic acid). We will record if women are also taking metformin. All of this will be discussed carefully with the participants and all participants will be advised that participating just once will still give us valuable data.

5. Eligibility

Inclusion Criteria

Inclusion criteria:
Cases

- Women with intrahepatic cholestasis of pregnancy, defined as pruritus in pregnancy in association with raised serum bile acids and in the absence of an alternative cause.
- Women with gestational diabetes mellitus (GDM) according to the diagnostic criteria used at the referring centre
- Non-pregnant parous females with previous ICP or GDM.
- Women who are able to give consent.
- Women >16 and <70 years of age.

Controls

- Pregnant women not affected by ICP or GDM .
- Non-pregnant parous females with previous uncomplicated pregnancy.
- Women who are able to give consent.
- Women >16 and <70 years of age.

Exclusion Criteria

Exclusion Criteria:

- Males.
- Non-pregnant females with other medical disorders that can cause liver impairment, abnormal lipid or glucose metabolism in pregnancy, e.g. pre-eclampsia, acute fatty liver of pregnancy, pre-existing diabetes mellitus
- Pregnant females with a history of other medical disorders that can cause liver impairment, abnormal lipid or glucose metabolism in pregnancy, e.g. pre-eclampsia, acute fatty liver of pregnancy, pre-existing diabetes mellitus
- Women who are not able to give consent.
- Women <16 and >70 years of age.

6. Adverse Events

An **adverse event (AE)** is any untoward medical occurrence in a participant during the study participation days. An existing medical condition (unless it worsens on the study participation days) is not classed as an AE.

All AEs will be recorded in the notes of the participant and on an AE form

A **serious advent event (SAE)** is any untoward and unexpected medical occurrence or effect that:

- Results in death
- Is life threatening to mother and/or baby
- Requires hospitalization
- Results in persistent or significant disorder incapacity ability

All SAEs and action taken as a result will be recorded in the notes of the participant and on an SAE form. An SAE form should be completed and faxed to the Chief Investigator within 24 hours. All SAEs should be reported to the appropriate research ethics committee where in the opinion of the Chief Investigator, the event was:

- 'related' i.e. resulted from the administration of any research procedures; and
- 'unexpected', i.e. an event that is not listed in the protocol as an expected occurrence

Reports of related and unexpected SAEs should be submitted within 15 days of the Chief Investigator becoming aware of the event using the NRES SAE form for non-IMP studies.

Contact details for reporting SAEs

[name] – [name]

[contact] Attention: URGENT - [name]

Please send SAE forms to [name], Dept of Surgery & Cancer, [name]

It is not anticipated that there will be any increased risk of adverse events or serious adverse events in this study. However, it could be that a participant may have an unexpected reaction to the food they eat i.e. an allergic reaction and appropriate action will need to be taken in the event of this happening.

It is also possible that a participant may experience a vasovagal (fainting) episode during venepuncture and appropriate care of the participant will be implemented should this happen.

7. Statistics

- Data analysis will take place at the Institute of Reproductive and Developmental Biology, Imperial College, London. It will be undertaken by the research scientists with statistical advice from the divisional statistician.
- We will use conventional statistical analysis including tests of normal distribution and either Students T-test or the Mann-Whitney U test as appropriate.

8. Procedure for entry to the study, schedule for sample analysis and data recording

- The study will obtain ethics approval from NHS Research and Ethics Committee and Trust R&D prior to starting recruitment.
- Patient information sheets will be provided and informed consent obtained.
- Participants will be asked to give consent to have their medical records examined by members of the research group. This will be undertaken in order to check any previous data that maybe of relevance to the study e.g. previous history of ICP or GDM
- The personal addresses telephone numbers and possibly e-mail addresses of participants are kept on file by the research group for future reference. This information is stored in a locked filing cabinet in a room within the research centre that is locked when not in use. Access is only granted to members of the research group.
- The personal data of the participants is also stored on a university computer. The computer is non net-worked and it is password protected. Access is only available to members of the research group
- Samples are linked-anonymised when they come into the laboratory for processing. The codes are kept in the PI's room ([name]) and only members of the research team have access to the coding book.
- Samples may be made available to collaborators, but these will be linked-anonymised and written consent from the participant will be obtained. If participants do not want their samples to be made available to collaborators they will have the option to opt out of this.
- Personal data is stored in a locked filing cabinet in a different building within a locked filing cabinet in the research centre. Any data relating to results are also coded and retained on a non net worked computer.

- Only members of [name] research team who are involved with the study will have access to the personal information included in the questionnaire. They will also have access to the medical records of the participants but only with the signed consent of the participants.
- Relevant data such as blood results may also be made available to collaborators, but this will be in a linked anonymised format, and written consent from the participant will be obtained.

9. Regulatory Issues

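### Should Section 4 divide the 40 non-pregnant cases between previous ICP and previous GDM?

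*Protocol*

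**What the plan says.** Protocol Section 4 (Study design) states two recruitment aims in consecutive sentences. For non-pregnant women: "In the non pregnant group we aim to recruit 40 women and 40 matched controls". For pregnant women: "In the pregnant women with and without ICP or GDM we aim to recruit 40 in each group together with matched controls".

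Section 4 then defines Group 1, the non-pregnant women, so that its affected members may have had ICP, GDM or both in an earlier pregnancy. Section 5 (Eligibility) agrees and admits as cases "Non-pregnant parous females with previous ICP or GDM". Neither section gives a number, minimum or quota by history.

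Two statements of purpose bear on these women. Section 2 (Hypothesis) expects "That there are abnormalities in bile acid, lipid and glucose homeostasis in women who have previously had ICP compared to controls". The synopsis objective is wider and asks whether women affected by ICP and GDM are "predisposed towards developing metabolic disease in pregnancy and in later life". On recruitment, Section 4 says: "Non-pregnant females may be identified through organisations such as ICP Support". It also allows posters and referral by clinicians and nurses.

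**The concern.** On a first reading the two targets look inconsistent. The pregnant target is stated per group, while the non-pregnant one is a single number covering two different histories. Taken literally, 40 women with a GDM history and none with an ICP history would meet it, and so would the reverse.

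The Section 2 hypothesis needs women with previous ICP. The synopsis objective also needs women with previous GDM. The reason the Background gives for including GDM does not settle the balance, because it concerns women who are currently pregnant: "This will enable us to evaluate the impact of cholestasis on the onset of diabetes mellitus in pregnant women".

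What is at stake is precision. If few of the 40 have one of the histories, the comparison of that history with controls will be imprecise. A statistical analysis plan can choose the contrasts but cannot change who was enrolled.

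**Working it through.** **1. Can the stated target be reproduced?** No. The protocol gives no significance level, power, effect size or SD behind the 40 and 40, so the figure can be neither confirmed nor called wrong.

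**2. Is the contrast with the pregnant target real?** Not securely. The sentence on pregnant women does not define its groups. The groups that Section 4 goes on to name are Groups 1, 2 and 3, and both pregnant ones (2 and 3) themselves combine ICP and/or GDM. If those are the groups meant, the pregnant target is just as undivided by condition. A reading by condition is also possible, and the text does not decide between them.

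**3. Which analyses depend on the mix?**
- Section 2: the only hypothesis on previously affected women is previous ICP against controls. There is no counterpart for previous GDM.
- Section 3: the objective concerns ICP, GDM and uncomplicated pregnancies, and the primary and secondary outcomes concern mother and fetus. None clearly depends on the non-pregnant mix.
- Section 1 (Importance): it calls a predisposition outside pregnancy unknown for women with ICP, but takes a raised later risk of type 2 diabetes after GDM as established. The open non-pregnant question is therefore chiefly the ICP one.
- Section 7 names two-sample tests and does not direct the analyst to pool the histories.

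**4. How much precision is at stake?** Assumptions: equal SDs, a two-sided 95% interval, and an unpaired comparison of k women of one history with all 40 controls. Half-width in SD units = t(0.975, k+38) × √(1/k + 1/40).

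| k | √(1/k + 1/40) | Half-width |
|---|---|---|
| 40 | 0.2236 | 0.445 |
| 30 | 0.2415 | 0.482 |
| 20 | 0.2739 | 0.548 |
| 13 | 0.3193 | 0.641 |
| 10 | 0.3536 | 0.711 |

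If each case is compared only with her own matched control, half-width = t(0.975, k−1) × √(2(1−ρ)/k), where ρ is the assumed within-pair correlation.

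| Pairs | ρ = 0 | ρ = 0.5 |
|---|---|---|
| 40 | 0.452 | 0.320 |
| 30 | 0.528 | 0.373 |
| 20 | 0.662 | 0.468 |
| 10 | 1.012 | 0.715 |

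For power, assume a two-sided 0.05 level and a true difference of 0.63 SD, which 40 against 40 detects with about 80% power. Against 40 controls, power is 74% with 30 cases, 63% with 20 and 43% with 10.

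**5. What bounds the loss?** Women with both histories count in either comparison. If b of the 40 have both, then (number with ICP) + (number with GDM) = 40 + b, which is at least 40. At least one history therefore has 20 or more women, and in the unpaired comparison its half-width is at most 0.55 SD. With 30 ICP cases the ICP interval is 0.482/0.445 = 1.08 times as wide as with 40. With 10 it is 0.711/0.445 = 1.60 times as wide.

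**The case for a change.** The strongest case for a change is that the protocol itself sets this target and recruits against it, so the gap cannot be repaired at the analysis stage. The two statements of purpose draw on different women, and one sentence would settle the matter. At 10 women of a given history the unpaired interval is about 60% wider than at 40, which is not trivial. The patient-organisation route probably favours ICP, but no yield is stated, and if ICP does dominate, the imprecision moves to the GDM part of the synopsis objective.

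The textual part of this stands: no mix is stated anywhere, and the arithmetic is right. The consequence is weaker. The splits are hypothetical, since none comes from the protocol. Later-life GDM rests on one broad synopsis sentence with no hypothesis or listed outcome behind it. The figure of 0.71 for a minority GDM group is a worst case under a 30/10 split, because it counts only women without ICP. Writing down a split would not improve precision unless recruitment changed, and a quota could slow enrolment of whichever history is harder to find. The Background puts ICP at about 0.7% of women in the UK.

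**Conclusion.** No change follows. Section 4 leaves open how the 40 non-pregnant cases divide between previous ICP and previous GDM, but it contradicts nothing: the Group 1 definition and the eligibility criteria agree, and the pregnant target is not a clear counter-example. An analyst would follow Section 2, compare women with previous ICP with controls, and report previous GDM separately with whatever precision the numbers allow. That is a sound reading of the plan, and the mix of histories does not in itself bias either comparison.

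The cost is limited to precision. The unpaired half-width goes from 0.45 SD with 40 women of a history to 0.48 with 30, 0.55 with 20 and 0.71 with 10, assuming equal SDs and use of all 40 controls. With 30 or more ICP women, the comparison that Section 2 names loses little. A sentence giving the intended mix would be a harmless clarification, but no result is shown to be wrong without it.

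### Controls are described as matched, but the only comparisons named do not use the matching; if the matching is effective, precision is given up

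*Protocol*

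**What the plan says.** The protocol describes its controls as matched in three places. The eligibility entry of the opening summary reads "Pregnant and non pregnant women who have been affected by ICP and GDM together with matched controls". Section 4 (Study design) says of the non-pregnant group "In the non pregnant group we aim to recruit 40 women and 40 matched controls", and of the pregnant groups "we aim to recruit 40 in each group together with matched controls". Section 4 also states "The study will be a case-control study".

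Nowhere does it say which factors are matched on, or whether matching is individual (each case tied to a particular control) or by frequency. For the pregnant groups it does not give the ratio of controls to cases.

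Section 7 (Statistics) describes the analysis in general terms, "We will use conventional statistical analysis including tests of normal distribution", and names the comparison as "either Students T-test or the Mann-Whitney U test as appropriate". No paired t-test, Wilcoxon signed-rank test, matched-set model or adjustment for matching factors is named. Section 7 adds about the analysis: "It will be undertaken by the research scientists with statistical advice from the divisional statistician".

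**The concern.** Section 4 and section 7 do not fit together. Matching is done so that cases and controls resemble each other on factors related to the outcome. If it works, it induces positive correlation between matched women. A test for independent samples leaves that shared variation in its error term, so its standard error exceeds the true sampling variability of the difference. The confidence interval is then wider than it need be and the test runs below its nominal level.

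The stake is clearest in the non-pregnant group. It addresses the second hypothesis, on abnormal bile acid, lipid and glucose homeostasis in women who previously had ICP, and the background section says this is unknown. These women attend once, so the issue is purely case-control matching, separate from any question of repeated visits. With 40 per side and no stated power calculation, a false null is a real possibility, and avoidable loss of precision makes it likelier. Eligibility runs from above 16 to below 70 years. If age were a matching factor, it could account for a fair share of the variation in lipids and glucose.

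**Working it through.** **Inputs from the protocol.** 40 cases and 40 matched controls in the non-pregnant group (section 4); Student's t or Mann-Whitney (section 7). The protocol states no alpha, power, effect size, SD or within-pair correlation, so there is no planned figure to reproduce.

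**Assumptions.** Two-sided alpha 0.05; 40 complete individual pairs analysed as one comparison; outcome SD 1; true difference d in SD units; within-pair correlation r, shown over a range.

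**Formulas (normal approximation).**
- Standard error used by the unpaired test: SE0 = sqrt(2/40) = 0.2236.
- True standard error of the difference under matching: SE0 × sqrt(1 − r). The unpaired SE is therefore too large by a factor 1/sqrt(1 − r).
- True type I error of the unpaired test: 2 × [1 − Φ(1.96/sqrt(1 − r))].
- Power, unpaired test on matched data: Φ((d/SE0 − 1.96)/sqrt(1 − r)).
- Power, paired test: Φ(d/(SE0 × sqrt(1 − r)) − 1.96).

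**Worked example, d = 0.5, r = 0.2.** d/SE0 = 0.5/0.2236 = 2.236 and sqrt(0.8) = 0.894. Unpaired: (2.236 − 1.96)/0.894 = 0.309, power 62.1%. Paired: 2.236/0.894 − 1.96 = 0.54, power 70.5%.

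**Results at d = 0.5.**

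| r | Unpaired SE too large by | True type I error | Power, unpaired | Power, paired |
|---|---|---|---|---|
| 0 | 0% | 5.0% | 60.9% | 60.9% |
| 0.1 | 5% | 3.9% | 61.4% | 65.4% |
| 0.2 | 12% | 2.8% | 62.1% | 70.5% |
| 0.3 | 20% | 1.9% | 62.9% | 76.2% |
| 0.5 | 41% | 0.6% | 65.2% | 88.5% |

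**Check by simulation** (40,000 runs for the t-tests, 8,000 for Mann-Whitney). At r = 0.2: unpaired t 60.8%, paired t 68.1%, Mann-Whitney 58.4%. At r = 0.5: unpaired t 63.6%, paired t 86.7%, Mann-Whitney 60.1%. Type I error at r = 0.5: 0.7% for unpaired t and 0.5% for Mann-Whitney. The approximation runs one or two points high for power; the pattern is the same.

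**Is the loss due to the matching or to ignoring it?** Compare the unpaired test on unmatched data with the same test on matched data:

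| d | Unmatched | Matched, r = 0.2 | Matched, r = 0.5 |
|---|---|---|---|
| 0.3 | 26.8% | 24.5% | 19.1% |
| 0.4 | 43.2% | 42.4% | 40.4% |
| 0.5 | 60.9% | 62.1% | 65.2% |
| 0.63 | 80.4% | 83.1% | 88.7% |

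The sign changes where unpaired power is 50%, at d = 1.96 × 0.2236 = 0.44. Below that, matching lowers the power of the unpaired test; above it, matching raises it. The paired test has more power than the unpaired test at every d in the table whenever r is positive.

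**The case against.** The strongest reply is that section 7 does not fix an unpaired analysis. It does not call the t-test unpaired, its list of methods is open, the choice is to be made as appropriate, and a statistician will advise. The exact form of a test is often left to the SAP, which is not at hand. Part of this stands: the two-sample reading is certain for Mann-Whitney but only implied for the t-test. It does not dispose of the point, because the protocol chose to name its comparisons. The non-parametric partner of a paired t-test would be the signed-rank test, yet the one named is for independent samples. Neither the open wording nor the promised advice supplies a matched method.

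Second, individual pairing is not established. Equal numbers do not make pairs, and the recruitment text describes no step that ties a given control to a given case. This stands. Under frequency matching there are no pairs and the paired power figures do not apply directly. The direction of the argument survives, since an unadjusted test still leaves variation due to the matching factors in the error term.

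Third, the effect depends on an unknown correlation. This also stands. At r = 0.1 the gap is only about 4 points of power and at r = 0 there is none. At r = −0.1 the unpaired standard error would be about 5% too small and the type I error 6.2%.

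A reader might go further and infer that standard errors will be too large as a matter of fact, or that matching itself reduces the chance of finding a difference. The protocol supports neither. The first needs positive within-set correlation, for which it gives no figure. The second holds only below d = 0.44 and reverses above it; the cost that matters comes from leaving the matching out of the analysis.

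**Conclusion.** The point holds in conditional form. The design specifies matched controls and the named comparisons do not use the matching. If matching induces positive correlation in the outcome, those tests are conservative. For 40 individual pairs and a 0.5 SD difference, they give up about 4, 8 and 23 points of power at correlations of 0.1, 0.2 and 0.5. The correlations, the effect size and the pairing are all assumptions, not figures from the protocol.

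With positive correlation the consequence is lost precision. False positive findings are not made more likely, and in complete 1:1 pairs the mean difference is identical under either analysis. It does not invalidate the study. The sponsor should still act, because the remedy is nearly free and the groups are small.

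**What to change.** In section 4, state for each case group the type of matching (individual or frequency), the matching factors and the ratio of controls to cases. This comes first, because the choice of analysis depends on it.

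In section 7, replace the sentence naming the tests so that case-control comparisons use the matching:
- **Individual matching:** a paired t-test on differences (log scale where suitable) or the Wilcoxon signed-rank test for 1:1 pairs, or a model with a matched-set effect, which also handles other ratios.
- **Frequency matching:** a linear model that includes the matching factors.

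Report the mean difference or ratio with its 95% confidence interval in either case.

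The cost is wording, plus recording which control belongs to which case if matching is individual. One small downside is that a case without a usable control drops out of a strictly paired test; the model-based analysis avoids this. If matching turns out to be uninformative, the penalty is slight: in the simulation at zero correlation and d = 0.5, the paired t-test had 58.8% power against 59.9% unpaired.
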